This method defines a hierarchical ordinal categorical response variable, for which a continuation logit model (Agresti 2002) will be used to perform separate logistical regression analyses adjusting for baseline risk factors including ERT status (ERT-naïve or ERT-experienced), duration of prior alglucosidase alfa (only for ERT-experienced subjects), gender, and baseline age.

The results of these separate logistic regression analyses are then pooled to test the overall null hypothesis that treatment with ATB200/AT2221 is less effective than alglucosidase alfa/placebo with respect to either the positive composite response (ie, significant improvement) or the negative response (ie, minor/no improvement). The inter-group comparison will be based on the combined analysis of comparisons of the positive response rates of significant improvements and the negative response rates of minor/no improvement.

Additional details regarding the separate logistic regression analyses and test against the overall null hypothesis are described below.

The “significant improvement” response category is considered as positive response, the “moderate improvement” category is considered as stable response, and “minor/no improvement” is considered as negative response. Treatment (ie ATB200/AT2221) is expected to have high positive responses and low negative responses, while the control (ie, alglucosidase alfa/placebo) is expected to have high negative responses and low positive responses). Separate logistic regression models are used to analyze and test (1) positive responses vs. not positive responses (where “not positive responses” includes the “moderate improvement” and “minor/no improvement” categories; (2) negative responses vs. stable responses, conditional on subjects who are not positive responders.

The respective hypotheses for Test 1 and Test 2 are stated as follows: $H_{10}: \delta_1 \leq 0$ vs. $H_{1A}: \delta_1 > 0$ and $H_{20}: \delta_2 \leq 0$ vs. $H_{2A}: \delta_2 > 0$, where δ_1 and δ_2 are the effect sizes for comparing treatment to control for Test 1 and Test 2 respectively.

Let the logistic regression model for Test 1 be:

$$\text{logit}(p_{1,Positive}) = \ln \frac{p_{1,Positive}}{p_{1,Not pos}} = \beta_{1,0} + \beta_{1,1} \text{TRT} + \beta_{1,2} \text{ERT} + \beta_{1,3} \text{DUR} + \beta_{1,4} \text{SEX} + \beta_{1,5} \text{AGE}$$

and Test 2 be:

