$$\text{logit}(p_{2,Negative}) = \ln \frac{p_{2,Neg}}{p_{2,Stable}} = \beta_{2,0} + \beta_{2,1} \text{TRT} + \beta_{2,2} \text{ERT} + \beta_{2,3} \text{DUR} + \beta_{2,4} \text{SEX} + \beta_{2,5} \text{AGE}$$

For any coefficient β , the Wald statistic is given by $Wald = b/se_b$, where b is the estimate for β and se_b is the standard error for β , and the Wald statistic is approximately normally distributed. Therefore, in testing the null hypothesis about the treatment effect, say $\beta_{1,2} = 0$ (for Test 1), the test statistic for treatment effect is: $(b_{1,2} - 0)/se_b = b_{1,2}/se_b$.

Let $Z_1 = b_1/se_{b_1}$ and $Z_{2/1} = b_{2/1}/se_{b_{2/1}}$ be the test statistics for testing treatment effect in Test 1 and Test 2 respectively, where Z_1 and $Z_{2/1}$ are standardized to have standard normal distributions (so that each has mean = 0 and variance = 1).

The inter-group comparison is based on the combined analysis of the positive response rates of significant improvements and the negative response rates of minor/no improvement. The overall null and alternative hypothesis ($H_0: H_{10} \cap H_{20}$) is tested against the alternative hypothesis ($H_A: H_{1A} \cup H_{2A}$) based on the combination test statistic:

$$Z = \frac{w_1}{w_1+w_2} Z_1 + \frac{w_2}{w_1+w_2} Z_{2/1}, \text{ where } w_1 \text{ and } w_2 \text{ are weights (constants) for the random}$$

variables Z_1 and $Z_{2/1}$ respectively (Rpatel 2019). The weights, w_i , represent the information fraction in test i . The expected value of Z is given by:

$$E(Z) = \frac{w_1}{w_1+w_2} E(Z_1) + \frac{w_2}{w_1+w_2} E(Z_{2/1}) = 0, \text{ under } H_0.$$

Assuming independence of Z_1 and $Z_{2/1}$, the variance of Z is given as:

$$\begin{aligned} Var(Z) &= \left(\frac{w_1}{w_1+w_2}\right)^2 Var(Z_1) + \left(\frac{w_2}{w_1+w_2}\right)^2 Var(Z_{2/1}) \\ &= \left(\frac{w_1}{w_1+w_2}\right)^2 + \left(\frac{w_2}{w_1+w_2}\right)^2 \end{aligned}$$

Inference is based on the standardized score Z_w , where

$$Z_w = \frac{\frac{w_1}{w_1+w_2} Z_1 + \frac{w_2}{w_1+w_2} Z_{2/1}}{\left[\left(\frac{w_1}{w_1+w_2}\right)^2 + \left(\frac{w_2}{w_1+w_2}\right)^2\right]^{1/2}}$$

follows the standard normal distribution under the null hypothesis. A 1-sided p-value for testing against the overall null hypothesis H_0 is given by $p = 1 - \Phi(z_w)$, where $\Phi(\cdot)$ is the cumulative distribution function of a random variable that follows the standard normal distribution.

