  lsmeans TRTPN / OM s alpha=0.05 cl diff; ** Obtain lsmeans and lsmean  
differences;  
  
  lsmestimate TRTPN "Treat vs. Control at Week 52" 1 -1 / upper  
  testvalue=0; **Get treatment diff and 1-sided p-value at W52 *;  
  
  lsmestimate TRTPN `Treat vs. Control at Week 52' 1 -1 / testvalue=0  
  alpha=0.05 cl; **Get treatment diff, 2-sided p-value, 95% CIs at W52*;
```

Sample Code for the Analysis of Composite Endpoint

```
*****  
* Implement separate logistic analyses for positive responses and *  
* negative responses, and then combine the two results using weights. *  
*  
* Assume input dataset (COMPOS) is structured as below, and has the *  
* following variables: RESPONSE, TRTPN, ERTSTA, DUR, SEX, AGEBL *  
*  
  1 1 N 2.4 F 0  
  3 1 N 3.5 M 0  
  1 1 E 2.7 M 37  
  0 2 N 5.6 F 0  
  3 1 E 7.0 M 67  
  3 2 N 2.0 F 0  
  2 1 E 4.1 M 64  
  1 2 N 4.8 M 0  
  0 2 E 7.7 F 28  
  3 1 E 5.5 F 32  
  2 2 E 6.3 F 48  
  . . . . .  
  
* RESPONSE variable = composite response with values 0, 1, 2, 3 *  
* TRTPN = Treatment group (1 = new treatment, 2 = control) *  
* ERTSTA = ERT status (Experienced or Naïve) *  
* DUR = duration of ERT: value for ERT-experienced, and 0 for naïve.*  
*****;  
  
** Analysis of positive responses vs. not positive responses **;
```

```
data comp1;
  set compos;
  if response=3 then resp1='Y';
  else resp1='N';
run;

** Analysis of stable responses vs. negative responses;
data comp2;
  set compos;
  if response=3 then delete;
  if response=2 then resp2='Y';
  else resp2='N';
run;

** Run two separate logistic regression models **;
ods output ParameterEstimates=test1;
proc genmod data=comp1;
  class TRTPN ERTSTA SEX;
  model resp1(event='Y') = TRTPN ERTSTA DUR SEX AGEBL / dist=binomial
                        link=logit type3;
run;

ods output ParameterEstimates=test2;
proc genmod data=comp2;
  class trt ert;
  model resp2(event='Y') = TRTPN ERTSTA DUR SEX AGEBL / dist=binomial
                        link=logit type3;
run;

data combo;
  merge test1(where=(level1='1') keep=level1 estimate stderr
              rename=(estimate=estimate1 stderr=stderr1))
        test2(where=(level1='1') keep=level1 estimate stderr
              rename=(estimate=estimate2 stderr=stderr2));
run;

** Calculate the weights, combine the test statistics and obtain the **;
** p-value using weight as the inverse of the standard error estimate **;
data combo2;
  set combo;
  w1=1/stderr1**2;
  w2=1/stderr2**2;
  z1=estimate1/stderr1;

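### MDRI Test 2 looks only at subjects who are not positive responders, so the pooled test can lose a benefit that mainly moves subjects from moderate to significant improvement

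*SAP*

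**What the plan says.** SAP 8.7 grades each subject from 0 to 3 on 6MWD, % predicted FVC and lower-extremity MMT. It treats grade 3 as positive, grade 2 as stable and grades 0–1 as negative. The between-arm inference is described as based on "the combined analysis of comparisons of the positive response rates of significant improvements and the negative response rates of minor/no improvement". Treatment "is expected to have high positive responses and low negative responses".

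Two logistic models carry this out. Test 1 is positive versus not positive in everyone. Test 2 is "negative responses vs. stable responses, conditional on subjects who are not positive responders". The Appendix 3 code matches that restriction: "if response=3 then delete". The two Wald statistics are combined with weights, taken as independent, and referred to the upper tail of the standard normal.

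The direction of Test 2 is not consistent. The equation printed in 8.7 models the log odds of negative against stable. Appendix 3 makes stable the event: "if response=2 then resp2='Y'". The stated alternative for Test 2 is an effect above zero in favour of treatment, which fits only the Appendix 3 direction.

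8.7 calls the analysis supplementary, and SAP 8.4 does not include it in the tested hierarchy.

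**The concern.** The stated question concerns two rates, each with all subjects of the arm as denominator. Test 2 answers a different one: among those who did not reach the top category, what share is negative? If treatment lifts subjects out of the moderate category, the treated remainder holds relatively more negatives even when no additional subject is negative. Test 2 then scores that gain as neutral or as harm, and the pooled statistic sets it against the gain in Test 1.

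At stake is the planned totality-of-evidence support for clinical benefit. It could show nothing, with an apparently adverse Test 2, in a trial where positive responses rose and negative responses did not.

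**Working it through.** **Inputs.** The SAP gives no rates, effect or power for the MDRI, so there is no MDRI figure to reproduce. Arm sizes follow SAP 4.3: about 110 randomised 2:1 gives 73:37, and 66:33 evaluable. The primary power claim for 66:33 (about 90% at effect size 0.7) does reproduce, at 90.2% from the noncentral t. Category rates below, as positive/moderate/negative, are assumptions.

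**Formulas (Appendix 3 direction, unadjusted).** b1 = difference in log odds of positive versus not positive. b2 = difference in log odds of stable versus negative among non-positives. SE² = sum of reciprocal cell counts. Z = b/SE, w = 1/SE². Zw = (w1·Z1 + w2·Z2)/√(w1² + w2²).

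**Worked case (b): treated 35/25/40, control 10/50/40.** The negative rate is 40% in both arms.
- Negative share among non-positives: 40/65 = 61.5% treated, 40/90 = 44.4% control.
- b1 = ln[(0.35/0.65)/(0.10/0.90)] = 1.578. SE1² = 1/25.55 + 1/47.45 + 1/3.7 + 1/33.3 = 0.361. Z1 = 2.63.
- b2 = ln[(0.25/0.40)/(0.50/0.40)] = −0.693. SE2² = 1/18.25 + 1/29.2 + 1/18.5 + 1/14.8 = 0.211. Z2 = −1.51.
- w1 = 2.77 and w2 = 4.75, so Zw = (2.77·2.63 − 4.75·1.51)/5.50 ≈ 0.02, one-sided p about 0.49. Equal weights give (2.63 − 1.51)/√2 = 0.79.

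The whole Test 1 signal is lost, although nobody is worse off.

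**Simulation.** 40,000 multinomial trials per pattern, 73:37, one-sided 0.025. The comparator is the tie-corrected Wilcoxon test, which is the score test of the proportional-odds model.

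| Pattern, treated vs control | Negative share among non-positives | Mean Z2 | MDRI power | MDRI, equal weights | Ordinal test |
|---|---|---|---|---|---|
| (a) 35/35/30 vs 10/50/40 | 46.2% vs 44.4% | −0.15 | 16% | 37% | 61% |
| (b) 35/25/40 vs 10/50/40 | 61.5% vs 44.4% | −1.5 | 1% | 6% | 27% |
| (c) 60/10/30 vs 30/40/30 | 75.0% vs 42.9% | −2.3 | 25–26% | 3–4% | 50% |

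Test 1 alone has 84% power in (a), and the same in (b), which has the same positive rates. In (c), Test 2 is nominally significant for harm in 68% of trials although the negative rates are equal. With 66:33 the MDRI and ordinal figures are 14% vs 55%, 1% vs 24% and 22% vs 46%.

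**Separating the causes.** In (a) Test 2 is close to neutral, so the loss is mostly dilution plus weighting. The 1/SE² weights favour Test 2 when control positives are few. In (b) conditioning dominates. In (c) the weights favour Test 1 and soften the loss, so equal weights make it worse.

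**Other patterns (73:37).**
- Negatives fall as well: 30/30/40 vs 10/40/50 gives MDRI 11%, ordinal 41%; 30/40/30 vs 10/40/50 gives 49% and 75%.
- Common odds ratio 2.5, four assumed control patterns: mean Z2 is +1.3 to +1.75, MDRI 54–62%, ordinal 64–68%.
- Mainly negative-to-moderate: 10/60/30 vs 10/40/50 gives 47% and 41%; 25/50/25 vs 20/30/50 gives 58% and 55%.
- No effect: MDRI rejects in 1.7–2.0% of trials, ordinal in 2.4%. The correlation of Z1 and Z2 is 0.00.

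**The case against.** The case for leaving it alone has substance.

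- Conditioning is intrinsic to the continuation-logit model the SAP names, and it is what makes the independence assumption acceptable. That stands: the variance formula is sound under no effect.
- The SAP expects more positives and fewer negatives. When enough negatives also move up, Test 2 is neutral or favourable. That stands, and it limits how general the concern is.
- The direction of the problem depends on Appendix 3. With the event printed in 8.7, a moderate-to-positive shift adds to Test 1: power is 71% in (b) and 96% in (c). But that sign counts a real fall in negatives against the drug and contradicts the stated alternative for Test 2, so it is no defence. It does make the sign conflict the first thing to settle.
- SAP 8.8.5 already tests the proportion improving on both 6MWD and % predicted FVC, which is the positive category. A gain there would not be hidden. No comparison of negative rates is planned.
- Patterns (a) to (c) depart from proportional odds, and the ordinal test has only 27% power in (b). This is true; it is a better test for these patterns, not a strong one.

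A reader might infer that any drug turning moderate into positive responders will look harmful, or that Test 2 always cancels Test 1. The documents do not support that: they give no category rates, and the results above run from total loss to a small MDRI advantage.

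**Conclusion.** The concern holds in limited form. Test 2 does not compare the negative response rates that 8.7 says it compares. Under the benefit-oriented coding, a mainly moderate-to-significant shift can cost the pooled test part or all of the Test 1 signal. In the assumed patterns the power loss against an ordinal test is 45 points in (a), 26 in (b) and about 25 in (c). It is about 6 to 10 points under a common odds ratio, and reverses slightly when the effect is mainly negative-to-moderate.

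These sizes rest on assumed rates, no covariate adjustment and every subject being classified. They do not show inflated type I error or a threat to the primary or key secondary claims. The consequence is lost power and a misleading Test 2 in a supplementary analysis, so the change is advisable rather than essential.

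**What to change.** 1. Reconcile the Test 2 event and sign between 8.7 (negative) and Appendix 3 (stable).
2. Make the MDRI inference one cumulative-logit (proportional-odds) model of the ordered response, positive > stable > negative, in all ITT subjects. Keep the 8.7 covariates (ERT status, prior ERT duration, gender, age) and use the one-sided test of the common treatment log odds ratio.
3. Report unconditional positive and negative response rates by arm. The continuation-logit tests may stay as description.

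Removing the deletion step while keeping the present variance formula would not do. Redefining Test 2 as negative versus not negative in everyone gives a null correlation with Test 1 of about 0.44 (66:33, 20/35/45 in both arms). Treating the two as independent then raises the one-sided error to about 4.0%.

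The cost is SAP wording and shorter code, which SAP section 2 allows before database lock. The single odds ratio assumes a common effect at both cut points; the test stays valid under no effect, with slightly less power if the effect is only negative-to-moderate.

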8.8. Analysis of Other Secondary Endpoints

8.8.1. Motor Function Test

Motor function test endpoints (including % predicted 6MWD time to complete TUG, and time to complete individual GSGC components) will be summarized by treatment group and visit. The change from baseline to Week 52 will be analyzed and compared between the 2 treatment groups using an ANCOVA model on the ITT-LOCF population, similar to that for the key secondary endpoints. No supportive and/or sensitivity analyses will be performed for these motor function tests.

8.8.2. Muscle Strength Tests

Muscle strength test endpoints (including MMT and QMT) will be summarized by treatment group and visit for the lower extremity score, upper extremity score, total MMT score, and the proximal muscle group score. In addition, the change from baseline to Week 52 for each endpoint measure will be analyzed and compared between the 2 treatment groups using an

ANCOVA model on the ITT-LOCF population, similar to that for the key secondary endpoints. A plot of the LS mean (\pm SE) change from baseline over time will be provided by treatment group.

A supportive analysis for the MMT lower extremity (right/left hip flexion, right/left hip abduction, right/left knee flexion, and right/left knee extension) will be conducted. For this analysis, the number of subjects with changes in score of ≤ -3 , -2 , -1 , 0 , 1 , 2 , or ≥ 3 (from baseline to the Week 52 visit) will be tabulated for each body part, and then summed across all 8 body parts for each treatment group. For this analysis, subjects must have tested on the same muscles (right or left) at both baseline and post-baseline visit in order to determine the point change. The summed changes in scores by categories across the 8 body parts will then be summarized (by number and percentage) for each treatment group. No inferential comparisons will be performed. Similar summaries will be performed for the body parts associated with upper extremity (right/left shoulder abduction, right/left shoulder adduction, right/left elbow extension, and right/left elbow flexion), overall MMT (lower extremity and upper extremity combined), and the proximal muscle group.

No supportive or sensitivity analysis will be performed for the QMT scores.

8.8.3. Other Pulmonary Function Tests

The other pulmonary function test endpoints (ie, % predicted SVC, maximum VC [% predicted], % predicted MIP, % predicted MEP, and SNIP [% predicted]) will be summarized by treatment group and visit. In addition, the change from baseline to Week 52 for each endpoint will be analyzed and compared between the 2 treatment groups using an ANCOVA model on the ITT-LOCF population, similar to that for the key secondary endpoints. No sensitivity or supportive analyses will be conducted for these.

A plot of the LS mean (\pm SE) change from baseline over time will be provided for the pulmonary function test (PFT) endpoints by treatment group. In addition, the difference between sitting FVC and supine FVC results will be summarized by visit.

The % predicted SVC will be calculated as: $(\text{observed SVC results} / \text{predicted value}) * 100$, where the predicted value is obtained from the corresponding VCMax predicted value in the dataset

8.8.4. Patient-reported Outcomes

The total score and change from baseline in total score will be summarized for the R-PAct scale, EQ-5D-5L (ie, based on the quantitative EQ-VAS score), and PROMIS instruments. The change from baseline to Week 52 in the total score and the EQ-VAS score will be analyzed using an ANCOVA model on the ITT-LOCF population, similar to that for the key secondary endpoints. A plot of the LS mean (\pm SE) change from baseline over time will be provided for each of these PROs by treatment group. The EQ-5D categorical responses and the changes in the responses will be summarized by visit for each of the 5 dimensions.

Handling Baseline Missing Data for PROs:

For the PROs, missing baseline total scores will be handled similarly to that described for the multi-item endpoints in Section 6.3.1. That is, a missing baseline total score will be imputed with the average of all non-missing baseline total scores (from both treatment groups combined). If

the subject is only missing specific item(s) at baseline, the average of all non-missing values for that specific item (from both treatment groups combined) will be used.

Note: a missing baseline total score (or a missing individual item score) will only be imputed if the subject has at least 1 non-missing post-baseline total score (or individual item score).

Handling Post-baseline Missing Data for PROs:

For any PRO with a total score based on multiple items/questions, a missing post-baseline total score at a given visit will be handled using the “50% prorating rule” described below:

- If $\geq 50\%$ of items are available, the total score will be calculated and prorated as the average of the non-missing items multiplied by the total number of items expected (Haywood, Garratt et al. 2004);
- If $< 50\%$ of items are available, the total score will not be calculated, and it will be set to missing (in the ITT-OBS population). For the ITT-LOCF population, missing data will be imputed as described in Section 6.1.4.1 and Section 6.3.2.

For the SGIC, the responses for each of the 8 items will be summarized by treatment group and visit. Additionally, the response scale for each item at Week 52 will be divided into 3 categories (improving, stable, or declining) which reflect the functional status, and these will be summarized by treatment group.

For the PGIC, a summary of the response score will be provided by treatment group and visit.

8.8.5. Proportion Improving on Both 6MWD and % Predicted FVC

The proportion of subjects improving on both 6MWD and % predicted FVC (where definition of improvement is provided in Section 8.7) will be compared between the 2 treatment groups using a logistic regression model adjusting for baseline age, ERT status, gender, baseline height, and baseline weight. The number and percent of subjects improving will be presented for each treatment group, and the p-value for comparing between the 2 treatment groups and the 95% confidence interval for the treatment difference will be calculated from the logistic regression model.

8.8.6. Analysis of Pharmacodynamic Endpoints

For the pharmacodynamic endpoints/biomarkers (CK and urinary Hex4), the change from baseline and percent change from baseline at each visit will be summarized by treatment group. A line plot over time of the mean \pm SE for the change and percent change from baseline will be provided by treatment group. The change from baseline to Week 52 will be compared between treatment groups using the nonparametric randomization-based covariance analysis described in Section 8.5.1.2. Analysis will be performed on the ITT-LOCF population.

8.8.7. Immunogenicity

This study will assess anti-rhGAA antibodies and NAbs in subjects treated with ATB200/AT2221 and alglucosidase alfa. The effect of immunogenicity results on PK, efficacy, safety, and PD will be explored. Further details will be provided in the MSP mentioned in Section 3.3.5.3 for the analysis of immunogenicity and PD data.

- Total ADA, including titers, will be assessed using the ATB200 assay, regardless of what treatment arm the subject is in, because the assay is set up for use with either treatment.
- NABs (inhibition of rhGAA-mediated hydrolysis of 4-MU glucoside, inhibition of rhGAA-mediated hydrolysis of glycogen, and inhibition of rhGAA binding to CI-MPR (for ATB200 analysis only) will be assessed using ATB200 in the assays, regardless of the treatment arm, because the assays are set up for use with either treatment (with the exception of the CI-MPR assay).
- CI-MPR will be handled slightly differently as follows: All samples will be analyzed in the CI-MPR assay regardless of treatment arm, but data will be reported/used for further analysis only for subjects treated with ATB200 (the assay cannot be set up for use with alglucosidase alfa).
- GAA cross-reactivity (anti-rhGAA antibodies cross-reactive to alglucosidase alfa) is also included in the protocol and will be assessed regardless of treatment arm (Screen/confirm analysis only; ie, no titers will be assessed with the GAA assay).
- Anti-rhGAA IgE will be assessed as needed regardless of treatment arm.

